6.2 Target Volumes

Target volumes will be based on the postoperative conventional MRI, and high b-value diffusion as well as perfusion MRI. Pre-operative conventional MRI should be reviewed in correlation with the post-operative residual tumor bed as per standard of care. Target volumes for this treatment are as follows:

Gross tumor volume, conventional MRI (GTV Low): shall be defined as the area of enhancement plus surgical cavity on pre-radiotherapy T1-gadolinium enhanced MRI, as per standard practice. If the conventional MRI does not show any abnormal enhancement, the GTV_Low will include the surgical cavity alone, as per standard practice.

Gross tumor volume, high b-value DW-MRI and perfusion MRI (GTV^HCV perf): shall be defined as the area of abnormality on pre-radiotherapy high b-value diffusion MRI and perfusion MRI. The HCV target volume will be defined as previously published 18 on b=3000 s/mm² diffusion weighted imaging by a threshold technique (mean intensity plus 2 standard deviations) calculated from a volume of interest in the normal-appearing brain tissue in the contralateral brain from the tumor.

Clinical target volume, conventional MRI (CTV Low): GTV_Low will be expanded by 1.7 cm to account for microscopic disease extension, and edited out of normal structures (e.g. calvarium, falx) as per standard of care.

Clinical target volume, high b-value DW-MRI and perfusion MRI (CTV^HCV perf): CTV^HCV will be set equal to the GTV^HCV

Planning target volume, conventional MRI (PTV Low): CTV_Low will be expanded by a margin of 0.3 cm, to account for daily patient set-up variability

Planning target volume, high b-value DW-MRI and perfusion MRI(PTV_High): CTV^HCV_perf will be expanded by a margin of 0.3-0.6 cm, or as appropriate to account for registration and daily patient set-up variability.

6.3 Treatment Planning and Localization Requirements

Immobilization / Simulation: A treatment planning CT and/or MRI will be obtained with the patient in the same position and immobilization device as for treatment. All patients will be positioned and immobilized with individualized thermoplastic masks to ensure precise localization methods.

Treatment Planning: All patients will undergo MR-guided treatment planning with a high b-value diffusion MRI-defined boost volume. GTV definition, CTV definition, and PTV margin are as described above. CTV and relevant normal tissues will be outlined on planning scan slices. The PTV margins will ensure adequate dose coverage by correcting for variability in treatment set-up and registration variability. Intensity modulated radiotherapy (IMRT) or rapid arc plans will be used to achieve the highest prescription dose to the target, while minimizing dose to the normal brain and other critical structures. The tumor and critical organ constraints are described in further detail below.

Target Volume Coverage: PTV_Low will be treated with a prescription dose of 60 Gy in 2 Gy fractions over 30 fractions, with a minimum dose of 95% of the prescription dose. Additionally, the volume of PTV_Low receiving a dose > 105% of the boost PTV prescription dose will be minimized based on achieving the PTV Low dose prescription requirements.

PTV_High will be treated with a prescription dose of 75 Gy in 2.5 Gy fractions over 30 fractions. Minimum dose to PTV_High will be 95% of the prescription dose, and maximum dose should be no more than 105% of the prescribed dose (no plan that includes any dose greater than 110% will be accepted.)

Organs at Risk: The following critical normal tissues including the brain, brain stem, optic nerves, optic chiasm, and external surface will be outlined on the appropriate MRI/CT scans. Any compromises to the target because of physician decision to spare visual pathway or brainstem will be well-documented.

6.4 Radiation Toxicity

Toxicities will be assessed using diagnostic imaging and physical exam and neurologic testing including MMSE. Toxicities will be graded clinically according to Common Toxicity Criteria (CTC).

6.4.1 Acute

Expected acute radiation-induced toxicities include hair loss; erythema or soreness of the scalp; nausea and vomiting; dry mouth; altered taste; fatigue; temporary aggravation of brain tumor symptoms such as headaches, seizures, or weakness; ear complications such as plugging of the ears, decreased hearing, or redness (erythema).

6.4.2 Early Delayed

Possible early delayed radiation effects include lethargy, transient worsening of existing neurological deficits occurring 1-3 months after radiotherapy treatment.

6.4.3 Late Delayed

Possible late delayed effects of radiotherapy include cataracts, and or eye damage leading to blindness, radiation necrosis, radiation leukoencephalopathy, radiation vasculopathy, pituitary dysfunction, radiation-induced neoplasms, and damage to the brainstem leading to significant motor or sensory deficits or even death.

7.0 DRUG THERAPY

7.1 Temozolomide

7.1.1 Description: Temozolomide is a methylating agent belonging to a group of compounds, imidazotetrazinones. Its chemical name is 8-carbamoyl-3-methylimidazo [5,1-d]1,2,3,5-tetrazin-4*(3H)*-one.

7.1.2 Toxicology:

Likely toxicities (occurring in >20% of patients) include: fatigue, nausea, vomiting, alopecia, headache, seizure, constipation, lymphopenia, anorexia.

Common toxicities (occurring in 3-20% of patients) include: confusion, memory impairment, blurred vision, allergic reaction, abdominal pain, diarrhea, stomatitis, arthralgia, thrombocytopenia, insomnia, coughing, dyspnea, dry skin, erythema, pruritis, rash, taste perversion, fever, back pain, peripheral edema, somnolence, myalgias, anxiety, depression, breast pain, upper respiratory infection, pharyngitis, sinusitis, urinary tract infection, increased urinary frequency, anemia, neutropenia, thrombocytopenia, decreased WBC.

Rare but serious toxicities (occurring in fewer than 3% of patients) include: anaphylaxis, erythema multiforme, toxic epidermal necrolysis/Stevens-Johnson syndrome, *Pneumocystis jiroveci* pneumonia, interstitial pneumonitis, alveolitis, pulmonary fibrosis, prolonged pancytopenia, aplastic anemia.

Pharmacology

- 7.1.2.1 Mechanism of Action: Temozolomide undergoes chemical degradation at physiologic pH to form MTIC (3-methyl-[triazen-1-y1]) imidazole-4-carboxamide, the active metabolite of dacarbazine. The cytotoxicity of MTIC is thought to be primarily due to alkylation at the O6 position of guanine residues18 with additional alkylation occurring at the N7 position.
- 7.1.2.2 Pharmaceutical Data: Temozolomide is supplied in white opaque, preservative free, 2-piece, hard gelatin capsules of the following p.o. dosage strengths: 5 mg, 20 mg, 100 mg, 140 mg, 180 mg, and 250 mg. Capsules should not be opened or chewed. If capsules are accidentally opened or damaged, inhalation or contact with the skin and mucous membranes should be avoided.
- 7.1.2.3 Storage and Stability: The capsules are packaged in 30 cc 28 mm-48- Type I amber glass bottles (30 capsules/bottle) and should be stored between 2 and 30 degrees Centigrade. Capsules are stable for at least 30 months when stored in amber glass bottles at this temperature.
- **7.1.2.4 Supplier:** Temozolomide is commercially available.

7.1.3 Recommended Concurrent Temozolomide Dose Modification:

Recommended dose modifications are as follows:

A weekly CBCPD will be drawn during concurrent temozolomide and radiotherapy treatment. Dose reductions may be made at the discretion of the treating physician, standardly not less than 67% of the starting dose (50 mg/m²). Dose reduction, delay or discontinuation of temozolomide administration will be decided weekly according to hematologic and non-hematologic adverse events (AEs) as recommended below.* If the administration of temozolomide has to be interrupted, the radiotherapy will proceed normally. Missed doses of temozolomide will not be made up at the end of radiotherapy.

*If one of more of the following are observed

- ANC <1.5X10⁹/L
- Platelet count <100 X10⁹/L
- Grade 3 non-hematologic AE (except alopecia, nausea and vomiting while on maximum anti-emetic and fatigue)

Then treatment with concomitant temozolomide will be held until all of the following conditions are met:

- ANC ≥1.5X10⁹/L
- Platelet count ≥100 X10⁹/L
- Grade ≤ 1 non-hematologic AE (except alopecia, nausea and vomiting while on maximum anti-emetic and fatigue)

As soon as all of the above conditions are met, the administration of temozolomide will resume at the same dose as used initially.

If one of more of the following are observed:

- ANC <0.5X10⁹/L
- Platelet count <75 X10⁹/L
- Grade 4 non-hematologic AE (except alopecia, nausea and vomiting while on maximum anti-emetic, and fatigue)

Then temozolomide treatment concomitant with radiation will be permanently discontinued.

7.1.4.2 A CBCPD will be obtained prior to each cycle of adjuvant temozolomide. A nadir CBCPD count will be drawn on day 22 (+/- 5 day window) of each cycle. These lab tests may be drawn at laboratories outside the University of Michigan provided the results sent to University of Michigan for toxicity assessment and dose modification.

Recommended dosing is based on adverse events during the prior treatment cycle. If multiple AE's are seen, the dose administered should be based on the dose reduction required for the most severe grade of any single AE.

Dose Level	Temozolomide Dose, mg/m2/day	Remarks
-2	100	Reduction if prior AE
-1	125	Reduction if prior AE
0	150	Starting dose cycle 1 (adjuvant)
+1	200	Escalated dose at cycle 2, for cycles 2-12 in absence of AE

Delay

On day 1 of each cycle (within the prior 72 hours), ANC \geq 1.5 x 10⁹/L, platelet count \geq 100 x 10⁹/L and all treatment-related grade 3 or 4 non-hematologic AEs (except alopecia, nausea, and vomiting) must have resolved (to grade \leq 1). If AEs persists, treatment should be delayed by 2 weeks for up to 4 consecutive weeks. If, after 4 weeks of delay, all AEs have still not resolved: then any further adjuvant

Dose escalation

treatment with temozolomide should be stopped.

If, during the first cycle, all non-hematologic AEs observed were grade ≤ 2 (except alopecia, nausea and vomiting) and with platelets $\geq 100 \times 10^9 / L$ and ANC $\geq 1.5 \times 10^9 / L$: then the temozolomide dose should be escalated to dose level 1 and this dose should be used as the starting dose for subsequent cycles. If treatment after cycle 1 has to be delayed because of ongoing non-hematologic AEs of grade ≥ 2 , then no escalation is possible. If the dose was not escalated at cycle 2, then the dose should not be escalated in further cycles (3-12).

Dose reductions

If any non-hematologic AE observed was grade > 2 (except alopecia, nausea and vomiting) and/or if platelets < 50×10^9 /L and/or ANC < 1×10^9 /L, then the dose should be reduced by one dose level. For patients who would require dose reductions to a dose level < 100 mg/m2/day, temozolomide will be stopped. Also, if any of the same non-hematologic grade 3 AE recurs (except alopecia, nausea and vomiting) after reduction for that AE, then temozolomide will be stopped.

If any treatment-related non-hematologic AE observed was grade 4 (except alopecia, nausea and vomiting) then adjuvant temozolomide treatment should be stopped.

Subsequent cycles (3-12): Any dose reductions of temozolomide will be determined according to (1) non-hematologic AE during the preceding treatment cycle, as well as (2) the nadir (lowest/worst) ANC and platelet counts observed. No dose escalation should be attempted. The same dose reductions as for the second cycle should be applied.

Important: If the dose was reduced or delayed for adverse events, there will be no dose escalation.

The reason(s) for dose reduction and/or delay must be documented in the CRF.

Summary of Recommended Dose Modification or Discontinuation During Post-Radiation Temozolomide

	radiation remozolomiae		
Worst Non-Hematologic AE (except alopecia, nausea and vomiting)			
During the Previous Cycles			
Grade			

0-2	No dose modifications for non-hematologic AEs. Dose escalations (only for cycle 2) or reductions based on ANC and platelet counts are applicable.
3	Reduce by one dose level (except alopecia, nausea and vomiting). Dose modifications (escalations or reductions) based on ANC and platelet counts are not applicable. No further escalation is possible. If the same non-hematologic grade 3 AE recurs (except alopecia, nausea and vomiting) after reduction for that AE, then stop.
4	Stop (except alopecia, nausea and vomiting). Dose modifications (escalations or reductions) based on ANC and platelet counts are not applicable.

Nadir Values		Platelets				
≥ 1.5 x 10 ⁹ /L		≥100 x 10 ⁹ /L	50 - 99 x 10 ⁹ /L	< 50 x 10 ⁹ /L		
		Escalation to DL 1 (cycle 2 only)	Dose unchanged	Reduce by 1 dose level		
ANC	≥1 & <1.5 x 10 ⁹ /L	Dose unchanged	Dose unchanged	Reduce by 1 dose level		
	< 1 x 10 ⁹ /L	Reduce by 1 dose level	Reduce by 1 dose level	Reduce by 1 dose level		

Hematologic AE on Day 1 of Each Cycle (within 72 hours before)			
AE	Delay		
	Delay up to 4 weeks until all resolved. If unresolved after 4 weeks then stop. If resolved, dose delay/reductions based on non-hematologic AEs are applicable. If treatment has to be delayed for AEs, then no escalation is possible.		

Non-Hematological AE (except for alopecia, nausea and vomiting) on Day 1 of Each Cycle (within 72 hours before)				
Grade	Delay			
2-3	Delay up to 4 weeks until all resolved (to grade ≤ 1). If unresolved after 4 weeks, then stop. If resolved, dose delay/reductions based on ANC and platelets are applicable. If treatment has to be delayed for AEs, then no escalation is possible.			

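### Adjuvant temozolomide: the Delay paragraph holds a cycle only for grade 3 or 4 non-hematologic AEs, but the day-1 table holds from grade 2, so a persisting grade 2 AE at cycle 2 gets different advice

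*Combined protocol and SAP*

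**What the plan says.** All the text is in the combined protocol and SAP, section 7.1.4.2 (adjuvant temozolomide) and its summary tables.

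- **Delay paragraph.** Besides adequate ANC and platelets, it requires that "all treatment-related grade 3 or 4 non-hematologic AEs (except alopecia, nausea, and vomiting) must have resolved" to grade 1 or lower by day 1 of each cycle. If they persist, the cycle is delayed for up to 4 weeks, after which adjuvant temozolomide ends.
- **Dose escalation paragraph.** If every cycle 1 non-hematologic AE (with the same three exceptions) was grade 2 or lower, platelets were at least 100 x 10^9/L and ANC at least 1.5 x 10^9/L, "then the temozolomide dose should be escalated to dose level 1", which is 200 mg/m2/day. A further sentence bars escalation in one case: "If treatment after cycle 1 has to be delayed because of ongoing non-hematologic AEs of grade" 2 or higher.
- **Worst-AE summary table, grade 0-2 row.** "No dose modifications for non-hematologic AEs. Dose escalations (only for cycle 2) or reductions based on ANC and platelet counts are applicable".
- **Day-1 non-hematologic AE table, grade 2-3 row.** "Delay up to 4 weeks until all resolved (to grade ≤ 1). If unresolved after 4 weeks, then stop". The row adds that a delay for AEs rules out escalation. The table heading is not limited to treatment-related AEs.
- **Grade 4.** "If any treatment-related non-hematologic AE observed was grade 4 (except alopecia, nausea and vomiting) then adjuvant temozolomide treatment should be stopped".

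**The concern.** The Delay paragraph and the day-1 table both say when the next cycle may start, and both use a 72-hour window before day 1. They name different grades, and no rule says which takes precedence. A physician working from the paragraphs could escalate a patient whom the table would hold, and might later stop.

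The case is plausible. Section 7.1.2 lists fatigue among toxicities occurring in more than 20% of patients, without giving grades. Fatigue is exempt from the hold rule in the concurrent phase (section 7.1.3) but not in the adjuvant phase, so persisting treatment-related grade 2 fatigue falls exactly where the two rules differ. Section 10.1.4 lets outside physicians give adjuvant chemotherapy, and they may consult either the paragraph or the table. What is at stake is consistent dosing advice.

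**Working it through.** The plan gives no figure to reproduce here. The check is to take one patient through each set of rules.

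**The patient.** A treatment-related non-hematologic AE, other than alopecia, nausea or vomiting, peaked at grade 2 in adjuvant cycle 1 and is still grade 2 on day 1 of cycle 2. ANC is at least 1.5 and platelets at least 100 x 10^9/L, both in cycle 1 and on day 1. Cycle 1 was given at dose level 0, 150 mg/m2/day. Because the AE is treatment-related, the difference in attribution wording between paragraph and table plays no part.

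**Following the paragraphs.**
1. Delay paragraph: the AE is not grade 3 or 4 and the counts are adequate, so no hold is required.
2. Escalation paragraph, first condition: the worst cycle 1 AE was grade 2 and the counts are met, so escalation applies.
3. Escalation paragraph, exception: it applies only if treatment has to be delayed. Step 1 gave no delay, so the exception is not triggered.
4. Worst-AE table, grade 0-2 row: no modification for the AE, and cycle 2 escalation is open.
5. Result: cycle 2 starts on time at 200 mg/m2/day.

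**Following the day-1 table.**
1. Grade 2 falls in the grade 2-3 row, so the cycle is delayed for up to 4 weeks.
2. If the AE resolves to grade 1 or lower in that time, treatment resumes without escalation: 150 mg/m2/day, given that the counts require no reduction.
3. If it does not resolve, temozolomide stops.

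**Which threshold was meant.** The exception in the escalation paragraph speaks of a delay for ongoing AEs of grade 2 or higher. An AE that reached grade 3 in cycle 1 already fails the first escalation condition and calls for a dose reduction. The grade 2 part of that sentence therefore does separate work mainly when a persisting grade 2 AE causes a delay, as the table says. This points to the Delay paragraph as the text to correct.

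**Why the correction should read grade 2 or higher, not grade 2-3.** A grade 4 AE in the adjuvant phase ends temozolomide under its own rule. A grade 4 AE in the concurrent phase does less: "Then temozolomide treatment concomitant with radiation will be permanently discontinued". Such a patient could reach adjuvant cycle 1 with the AE unresolved, and the Delay paragraph is the explicit gate for that case. Keeping grade 4 within its wording preserves the gate.

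**The case against.** The strongest reply is that the section, read as a whole, already gives one answer. The Delay paragraph sets a minimum and does not tell anyone to treat through a grade 2 AE, so a physician who follows the table breaches nothing in it. The grade 0-2 row governs dose by worst past grade, while the day-1 table governs timing, and both can apply to one patient. Other wording leans towards the table: the exception in the escalation paragraph, the line ruling out escalation after any delay or reduction for AEs, the remark tying the 200 mg/m2 level to absence of AEs, and the proviso in section 10.1.3 that the increase depends on toxicity.

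Much of this stands. A reader might infer that the plan gives flatly opposite instructions with no sign of what was intended, and the documents do not support that. What remains is that the Delay paragraph states the wrong threshold. Each sentence ruling out escalation after a delay depends on a delay that this paragraph does not require for grade 2. The remark on absence of AEs names no grade, and the explicit escalation rule allows AEs up to grade 2.

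A second reply is that little hangs on it. The modifications are headed as recommended, adjuvant temozolomide follows standard care, and it is not among the departures from standard care listed in section 11.0. That also stands and limits the weight of the point.

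**Conclusion.** The inconsistency is real and is in the current text. For the patient described, cycle 2 is 200 mg/m2/day on time under the paragraphs. Under the table it is delayed, then given at 150 mg/m2/day if the AE resolves, or not given if it is unresolved at 4 weeks. This rests on adequate counts and on an AE that never exceeded grade 2. The section as a whole favours the table, so this is a drafting correction to recommended guidance and a minor point.

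Three stronger inferences are not supported.

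- A reader might infer an effect on 12-month overall survival. Nothing in the documents links this rule to the primary endpoint, and none is claimed.
- A reader might infer a large loss of cumulative dose by comparing a stopped patient with an escalated one. That assumes that a patient with persisting grade 2 toxicity would tolerate every later cycle at 200 mg/m2 without modification, which is a best case.
- A reader might infer a number of affected patients. The documents do not give the share with persisting grade 2 AEs, and the entry for fatigue gives neither grade nor duration.

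**What to change.** In the Delay paragraph, change the AEs that must resolve before day 1 from treatment-related grade 3 or 4 to treatment-related grade 2 or higher, keeping the existing exceptions. Leave the adjuvant grade 4 stop rule as it is. The paragraph then agrees with the day-1 table's threshold and with the escalation exception.

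The cost is one phrase, by amendment. Sample size, visits and analysis do not change. The clinical downside should be stated openly. In every adjuvant cycle, including cycle 1, a persisting treatment-related grade 2 AE such as fatigue would lead to a delay, no escalation at cycle 2, and a stop if unresolved at 4 weeks. The table already directs this. If the sponsor does not intend it, the alternative is to change the table row and the escalation exception.

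Whether the day-1 table should also be limited to treatment-related AEs is a separate clinical question for the sponsor. The correction to the Delay paragraph does not depend on it.

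### For a grade 4 non-hematologic adverse event not related to treatment, the adjuvant temozolomide text leads to a one-level reduction while the summary table says stop

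*Combined protocol and SAP*

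**What the plan says.** Section 7.1.4.2 sets the dose for each adjuvant cycle from what happened before it. Under its dose-reductions heading, the trigger "If any non-hematologic AE observed was grade > 2" (other than alopecia, nausea and vomiting) leads to the instruction "then the dose should be reduced by one dose level". That trigger carries no attribution condition. The stop rule follows: "If any treatment-related non-hematologic AE observed was grade 4 (except alopecia, nausea and vomiting) then adjuvant temozolomide treatment should be stopped".

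The table titled as a summary of recommended dose modification or discontinuation after radiation is indexed by the worst non-hematologic event. Its grade 4 row opens "Stop (except alopecia, nausea and vomiting", closes the parenthesis, and says nothing about attribution.

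The look-back wording differs as well. The text bases dosing on the prior cycle and, for cycles 3 to 12, on "non-hematologic AE during the preceding treatment cycle". The table heading says "During the Previous Cycles".

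**The concern.** Permanent discontinuation is the most consequential of the dose decisions in this section, and here it depends on which page is followed. A patient with a grade 4 non-hematologic event judged unrelated to treatment, for example one caused by the tumor, continues one level lower under the text and loses the drug under the table.

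The regimen is meant to be delivered uniformly. Section 11.1 plans a joint analysis with a second center that treats its patients identically, and the primary comparison is with a fixed historical rate. Two answers to one question do not support that uniformity. What is at stake is consistent conduct and the ability to reconstruct why a patient stopped, not the operating characteristics of the test.

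**Working it through.** No sample size, power or alpha figure depends on this, so the check sets the two rules side by side.

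**Inputs.** From the text of 7.1.4.2: grade above 2, any attribution, gives one level down; grade 4 and treatment-related gives stop; a reduction to below 100 mg/m2 gives stop. From the table: grades 0 to 2, no modification; grade 3, one level down; grade 4, stop. Dose levels are 200, 150, 125 and 100 mg/m2. Section 10.1.3 plans six adjuvant cycles. Alopecia, nausea and vomiting are excluded in both places, and blood counts are taken as normal.

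**Comparison.** Five grades by two relatedness states give 5 × 2 = 10 combinations. Relatedness is taken as yes or no, because section 7.1 does not say which of the five attribution categories in 12.1.4 count as treatment-related.

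| Worst grade | Treatment-related | Text | Table | Combinations |
|---|---|---|---|---|
| 0, 1 or 2 | yes or no | no change | no change | 6, agree |
| 3 | yes or no | one level down | one level down | 2, agree |
| 4 | yes | stop | stop | 1, agree |
| 4 | no | one level down | stop | 1, **conflict** |

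Agreement is 6 + 2 + 1 = 9 of 10.

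**Consequence for one patient.** Take an unrelated grade 4 event in cycle 1 at 150 mg/m2.
- Text: one level down, so 125 mg/m2 in cycle 2 once the day-1 conditions are met.
- Table: no cycle 2. Planned cycles lost: 6 − 1 = 5. The loss would be larger if the optional further cycles in 10.1.3 would have been given.
- For an event in cycle k, the planned cycles lost are 6 − k, so the gap shrinks as treatment goes on.
- If the patient is already at 100 mg/m2, a further reduction would go below the floor and the text also leads to stopping. The conflict disappears there.

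**Can the table be read as limited to related events?** Section 12.1.2 defines an adverse event without any judgment of causality, and 12.1.4 keeps categories for unlikely and unrelated events. The adjuvant text uses the treatment-related qualifier where it wants one (the day-1 rule and the stop rule) and leaves it out of the reduction rule between them. An unqualified entry in the table therefore includes unrelated events.

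**The case against.** The strongest reply is that this is a small mismatch between a full rule and its summary. The table calls itself a summary, the rules are labelled as recommendations, adjuvant temozolomide is given as standard care, and the text has the attribution test. The two sources agree on 9 of 10 combinations, and the documents give no frequency for unrelated grade 4 non-hematologic events. All of this limits the consequence, and the narrowness stands. It does not settle the conflict: no section says that the text prevails over the table, and two contradictory recommendations still leave the treating physician without an answer.

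A reader might go further in three ways that the documents do not support.

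- *Repeated reductions from one old event.* If the table were re-applied each cycle to the worst grade over every earlier cycle, a single grade 3 event in cycle 2 at 200 mg/m2 would give 150, 125 and 100 in cycles 3, 4 and 5 and a stop at cycle 6; the text gives 150 from cycle 3 on. But the heading does not say all previous cycles. The table's grade 3 row also has its own consequence for recurrence after a reduction, which fits one reduction per event. On that reading the path equals the text's. The plural is probably a drafting slip.
- *An effect on survival.* The 14.6 versus 12.1 months in section 1.0 compares radiotherapy plus concurrent and adjuvant temozolomide with radiotherapy alone. It does not isolate adjuvant cycles, still less early stopping after an adverse event.
- *Outside physicians or centers diverging.* Section 10.1.4 allows chemotherapy to be given elsewhere but does not say which page those physicians would use, and 7.1.4.2 has outside laboratory results sent to the study site for dose modification. The second center's protocol is not among the documents.

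**Conclusion.** The contradiction on grade 4 events is real and follows directly from the wording. It affects one of ten grade-by-relatedness combinations, and for a patient in that group it separates continuing at a lower dose from permanent discontinuation, with up to 5 of 6 planned cycles at stake. This rests on reading adverse event as section 12.1.2 defines it and on the absence of any precedence statement. The number of patients affected is unknown and may be small. No change in power, alpha or the 12-month survival estimate is claimed. The look-back difference is a minor inconsistency of wording. Which rule is clinically right is not judged here.

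**What to change.** Amend section 7.1 so that the grade 4 sentence in the text and the grade 4 row of the table carry the same attribution wording. The sponsor decides which version applies. State which attribution categories from 12.1.4 count as treatment-related. In the same edit, give the table heading and the text the same look-back period.

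Extend the existing CRF reason field. It is now required for dose reduction and/or delay; it should also cover stopping and the attribution of the triggering event. This is a small addition that routine collection would largely miss: under 12.1.1 adverse events are collected to 30 days after radiotherapy, while adjuvant treatment starts about 4 weeks after it, an overlap of roughly 30 − 28 = 2 days. The follow-up visits in 10.2 include toxicity notation, but the calendar does not link it to temozolomide decisions.

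The cost is a wording amendment to one sentence, one table row and one heading, plus the CRF extension. No extra visits are needed.
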